4.3. Life Style Guidelines

4.3.1. Contraception

All fertile male subjects and female subjects of childbearing potential who are, in the opinion of the investigator, sexually active and at risk for pregnancy with their partner(s), must agree to use a highly effective method of contraception consistently and correctly for the duration of the active treatment period and for at least 28 days after the last dose of investigational product. The investigator or his/her designee, in consultation with the subject and his/her legally acceptable representative/parent(s)/legal guardian, will confirm that the subject has selected an appropriate method of contraception from the list of permitted contraception methods (see below). At time points indicated in the [schedule of activities \(SOA\)](#), the investigator or designee will instruct the subject of the need to use highly effective contraception consistently and correctly and document the conversation, and the subject's affirmation, in the subject's chart. In addition, the investigator or his/her designee will instruct the subject to call immediately if the selected contraception method is discontinued or if pregnancy is known or suspected in the subject or partner.

Highly effective methods of contraception are those that, alone or in combination, result in a failure rate of less than 1% per year when used consistently and correctly (ie, perfect use) and include the following:

1. Established use of hormonal methods of contraception associated with inhibition of ovulation (eg, oral, inserted, injected, implanted, transdermal) provided the subject plans to remain on the same treatment throughout the entire study and has been using that hormonal contraceptive for an adequate period of time to ensure effectiveness.
2. Correctly placed copper-containing intrauterine device (IUD).
3. Male condom or female condom used WITH a spermicide (ie, foam, gel, film, cream, or suppository). For countries where spermicide is not available or condom plus spermicide is not accepted as highly effective contraception (eg, EU), this option is

not appropriate. (Note: In the UK and Belgium, a condom plus spermicide is not accepted as highly effective contraception).

NOTE: Sexual abstinence, defined as completely and persistently refraining from all heterosexual intercourse (including during the entire period of risk associated with the study treatments) may obviate the need for contraception ONLY if this is the preferred and usual lifestyle of the subject.

Also, all subjects who are, in the opinion of the investigator, sexually active and at risk for pregnancy with their partner(s), and are on background medications (including DMARDs) that require contraceptive measures according to the local drug label must meet those requirements during the study and after therapy for 3 months or for the duration specified in the local drug label.

4.3.2. Non-Pharmacologic Interventions

The subject may continue, add, or remove all non-pharmacological therapies, such as physical therapy, as indicated and deemed appropriate for his/her physical condition. For subjects with psoriatic arthritis, refer to [Section 5.5.2](#).

4.3.3. Vaccine and Exposure to Infections Guidelines

It is recommended that all study participants should be up-to-date with respect to standard of care vaccinations (as defined by their country health ministry) or JIA guidelines.

Vaccination with live components (e.g. live attenuated influenza vaccine, MMR (measles, mumps, and rubella) vaccine, or MMR-V (measles, mumps, rubella and varicella) vaccine) is prohibited within the 6 weeks prior to first dose of study drug. At the discretion of the investigator, subjects may be vaccinated with a live or live-attenuated vaccine at any time during the study only if tofacitinib is discontinued for a minimum of 6 weeks prior to vaccination and a minimum of 6 weeks after vaccination.

Inactivated vaccines, including inactivated influenza vaccine, pneumococcal conjugate vaccine and pneumococcal polysaccharide vaccines, may be administered to study subjects during the conduct of the study.

Administration of non-live COVID-19 vaccines that are fully approved or approved for emergency use is permitted during the study, provided that the vaccination is not part of another clinical study. Examples include, but are not limited to, mRNA vaccines, adenovirus vector vaccines and inactivated COVID-19 vaccine. If a participant receives a non-live COVID-19 vaccine during the study, it should be recorded as a concomitant medication and standard AE collection and reporting processes would be followed.

4.3.3.1 Varicella vaccination for participants enrolled from A3921165

Varicella vaccination is encouraged when appropriate, and if the participant is vaccinated, the first dose of study drug may not be administered until at least 4 weeks after vaccination.

For subjects who have not been vaccinated for varicella and did not have a positive VZV IgG Ab serology test at the A3921165 screening visit, evaluate the subject for varicella at every study visit. For those subjects who have been vaccinated or have a positive VZV IgG Ab serology test at screening, evaluate the subject for herpes zoster at every visit. Please refer to [Appendix 16](#) regarding the diagnosis and treatment of varicella and herpes zoster in study subjects.

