4.2. Exclusion Criteria

Subjects presenting with any of the following will not be included in the study:

For subjects who enroll outside the 14 day window of the EOS Visit of their qualifying/index study (Exclusion 13-15):

- 1. Blood dyscrasias, including:
 - a. Hgb <10 g/dL or Hct <33%;
 - b. WBC <3.0 x 10⁹/L;
 - c. Neutrophil count <1.2 x 10⁹/L;
 - d. Platelet count <100 x 10⁹/L;
 - e. Lymphocyte count of <0.75 x 10⁹/L.
- 2. Estimated glomerular filtration rate [GFR] <40 mL/min/1.73 m² calculated using Bedside Schwartz formula ([Appendix 5](#)) at the Screening Visit.
- 3. Aspartate aminotransferase (AST) or alanine aminotransferase (ALT) ≥1.5 times the upper limit of normal or any other clinically significant laboratory abnormality.

For all subjects:

4. Persistent oligoarthritis and undifferentiated JIA.
5. Current or recent history of uncontrolled clinically significant renal, hepatic, hematological, gastrointestinal, endocrine, pulmonary, cardiac, or neurological disease.
6. History of any other rheumatic autoimmune disease, other than Sjogren's syndrome.
7. History or current symptoms suggestive of any lymphoproliferative disorder, such as Epstein Barr Virus (EBV) related lymphoproliferative disorder, history of lymphoma, leukemia, or signs and symptoms suggestive of current lymphatic disease.
8. Infections:
 - a. Chronic infections.
 - b. Any infection requiring hospitalization, parenteral antimicrobial therapy or judged to be opportunistic by the investigator within the 3 months prior to the first dose of study drug.
 - c. Any treated infections within 2 weeks of baseline visit. (excluding those treated with topicals only).
 - d. A subject known to be infected with human immunodeficiency virus (HIV), hepatitis B or hepatitis C virus.
 - e. History of infected joint prosthesis with prosthesis still in situ.
9. History of recurrent (more than one episode) herpes zoster or a single episode of disseminated herpes zoster or a single episode of disseminated (both oral and genital lesions simultaneously, or widespread lesions not contained to oral or genital regions alone) herpes simplex.
10. Subjects taking potent and moderate cytochrome P450 3A4 (CYP3A4) inhibitors ([Appendix 6](#)).
11. Subjects taking potent and moderate CYP3A4 inducers ([Appendix 6](#)).

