12. Participation in studies of investigational compounds (excluding qualifying/index study with tofacitinib) within 4 weeks or 5 half-lives (whichever is longer) prior to the first dose of study drug. Subjects cannot participate in studies of other investigational compounds at any time during their participation in this study. Exposure to investigational biologics should be discussed with the Pfizer Medical Monitor.

13. Any prior treatment with non B cell-specific lymphocyte depleting agents/therapies [eg, alemtuzumab (CAMPATH®), alkylating agents (eg, cyclophosphamide or chlorambucil), total lymphoid irradiation, etc]. Subjects who have received rituximab or other selective B lymphocyte depleting agents (including experimental agents) are eligible if they have not received such therapy for at least 1 year prior to study baseline and have normal CD 19/20+ counts by FACS analysis.
14. Pregnant or nursing females are excluded.
15. Intramuscular or intravenous corticosteroids in the 4 weeks preceding first dose of study medication (oral corticosteroids permitted as per inclusion criterion).
16. Subjects who have been vaccinated with live or attenuated vaccines within the 6 weeks prior to the first dose of study medication. All study participants should be up-to-date with respect to standard of care vaccinations (as defined by their country health ministry). (See [Life Style Guidelines](#) for further information regarding avoidance of household contacts who may be vaccinated).
17. Use of prohibited prescription or nonprescription drugs and dietary supplements within 7 days or 5 half-lives (whichever is longer) prior to the first dose of study medication.
18. Herbal supplements must be discontinued at least 4 weeks prior to the first dose of study medication.
19. Subjects with a first degree relative with a hereditary immunodeficiency; IgA deficiency not exclusionary.
20. Subjects with a malignancy or with a history of malignancy with the exception of adequately treated or excised non-metastatic basal cell or squamous cell cancer of the skin or cervical carcinoma in situ.
21. Recent (within 28 days prior to first dose of study drug) significant trauma or major surgery.
22. Unwilling or unable to comply with the [Life Style Guidelines](#) described in this protocol.

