4.3.3.2 Guidance regarding Household Contact Vaccine-Related Exposure

In accordance with the Infectious Disease Society of America's guidance for vaccination in immunocompromised individuals, the following is a guide for study subjects and their household contacts.

- i. Immunocompetent individuals who live in a household with the study subject can safely receive inactivated vaccines based on the standard of care vaccination schedules for children and adults or for travel (as defined by their country health ministry) or JIA guidelines.
- ii. Individuals who live in a household with a study subject should receive influenza vaccine annually. They can receive either: (a) inactivated influenza vaccine or (b) live attenuated influenza vaccine (LAIV) provided they are healthy and otherwise eligible.
- iii. Healthy immunocompetent individuals who live in a household with a study subject should receive the following live vaccines based on the CDC annual schedule: combined measles, mumps, and rubella (MMR) vaccines; rotavirus vaccine in infants aged 2–7 months; varicella vaccine; and zoster vaccine. Also, these individuals can safely receive the following vaccines for travel: yellow fever vaccine and oral typhoid vaccine.
- iv. Oral polio vaccine (OPV) **should not be administered** to individuals who live in a household with a study subject.
- v. Study subjects should avoid handling diapers of infants who have been vaccinated with rotavirus vaccine for 4 week after vaccination.
- vi. Immunocompromised patients should avoid contact with persons who develop skin lesions after receipt of varicella or zoster vaccination until the lesions clear

Subjects should avoid exposure to vaccinated or infected persons and contact the Investigator promptly should they develop signs and symptoms of infections.

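### For entrants from A3921165, the protocol gives a 4-week minimum between varicella vaccination and first dose in one section and a 6-week bar on live vaccines in two others, with no exception stated

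*Protocol*

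**What the plan says.** Four places in the Protocol bear on the gap between a live vaccine and the first dose.

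- Section 4.3.3.1 is headed "Varicella vaccination for participants enrolled from A3921165". It encourages vaccination where appropriate and, for a participant who is vaccinated, says "the first dose of study drug may not be administered until at least 4 weeks after vaccination".
- Exclusion Criterion 16 (Section 4.2) rules out "Subjects who have been vaccinated with live or attenuated vaccines within the 6 weeks prior to the first dose of study medication". It stands in the block introduced by "For all subjects", which starts at Criterion 4. The separate lead-in for people enrolling more than 14 days after the index study mentions Criteria 13 to 15, not 16.
- Section 4.3.3, the parent of 4.3.3.1, sets the general rule for vaccines with live components and ends its list of examples with "MMR-V (measles, mumps, rubella and varicella) vaccine) is prohibited within the 6 weeks prior to first dose of study drug".
- Section 4.3.3.2, on household contacts, says that healthy contacts "should receive the following live vaccines based on the CDC annual schedule", and the list that follows includes "varicella vaccine; and zoster vaccine".

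**The concern.** The same event, varicella vaccination before the first dose, carries two different minimum intervals in current operative text. A site that works from the eligibility checklist will apply 6 weeks. A site that works from the section written for its A3921165 participants may apply 4. Two children with identical histories could then be handled differently.

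The interval governs when a JAK inhibitor is started after a live vaccine. It does so in the subgroup for which the protocol added skin examinations, weekly home checks and Appendix 16. Under that appendix, suspected varicella or zoster stops study drug, and unless it is ruled out the child leaves the study and the event is considered a serious infection. The primary objective is safety, and the SAP (Section 6.6) sets out incidence rates for serious infections and for herpes zoster. There is also a data-handling question: for a child first dosed on, say, day 35 after vaccination, the protocol does not settle whether an eligibility deviation has occurred.

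**Working it through.** There is no planned figure to reproduce. The check is a comparison of text plus a conversion from weeks to days.

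**Step 1: does the 6-week rule reach varicella vaccine?** Criterion 16 covers live or attenuated vaccines. Section 4.3.3.2 lists varicella vaccine as live, and Section 4.3.3 names MMR-V among its examples. On the protocol's own wording, the answer is yes.

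**Step 2: does the 6-week rule reach A3921165 entrants?** Criterion 16 is in the all-subjects block and contains no carve-out. Its only pointer to the Life Style Guidelines concerns contact with vaccinated household members. The answer is yes.

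**Step 3: is an exception written anywhere?** None was found. Inclusion Criterion 6 makes a useful contrast. There the protocol wants a different oral corticosteroid limit for A3921165 entrants and says so inside the criterion, then repeats it in Section 5.5.2 and Appendix 3.

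**Step 4: where do the rules diverge?** 4 weeks × 7 = 28 days; 6 weeks × 7 = 42 days; 42 − 28 = 14 days.

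| Days from varicella vaccination to first dose (A3921165 entrant) | Section 4.3.3.1 | Criterion 16 and Section 4.3.3 |
|---|---|---|
| Fewer than 28 | not met | not met |
| 28 to about 42 | met | excluded / prohibited |
| More than 42 | met | met |

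The upper edge is approximate because the protocol does not say whether day 42 itself counts as within 6 weeks.

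**Step 5: who can fall in the middle row?** Take the first dose as given on the day of the combined Screening/Baseline visit (an assumption), g days after the index study's end-of-study visit. The relevant vaccination dates then lie 28 − g to 42 − g days before that end-of-study visit. Section 6.1 expects rollover with g between 0 and 14.

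- At g = 0 the dates are 28 to 42 days before the end-of-study visit.
- At g = 14 they are 14 to 28 days before it.

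In both cases the vaccination would have taken place during the index study, whose vaccine rules are not in these documents. A vaccination after the end-of-study visit can fall in the window only if g exceeds 28 days, which requires the separate Screening and Baseline route. The documents give no count of such children.

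**The case against.** The strongest reply is that nothing conflicts. Section 4.3.3.1 is worded as a prohibition before 4 weeks, not as a permission at 4 weeks. A child who waits 6 weeks satisfies all three passages, so the stricter rule simply binds. The point about wording stands: a reader might infer that 4.3.3.1 positively authorises dosing at week 4, and the text does not say that. But if 6 weeks always governs, the 4-week sentence does no work and can only mislead a site that reads it alone.

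The second reply is that the specific rule overrides the general one. Section 4.3.3.1 names one vaccine and one source study, and the summary of changes describes it as an addition to align with A3921165, so it may well be deliberate. That is plausible but unstated, and it sets a lifestyle guideline against an unqualified exclusion criterion. The two replies also lead to opposite instructions for the same child, and the protocol gives no basis for choosing between them.

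The third reply concerns scale, and it stands. Given the expected rollover on the same day or within 14 days, few children may ever fall in the window.

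**Conclusion.** The discrepancy is real and should be corrected. For A3921165 entrants vaccinated against varicella about 28 to 42 days before first dose, the 4.3.3.1 interval is met while Criterion 16 excludes the child and Section 4.3.3 is breached. The window is 14 days. The number affected is unknown and may be small. Sample size, error rates and the planned summaries do not change. The conclusion rests only on current protocol text, including the protocol's own classification of varicella vaccine as live.

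Four stronger readings are not supported:

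- That every vaccinated A3921165 entrant is caught. A child vaccinated long before satisfies every rule, and one vaccinated fewer than 28 days before is barred by every rule.
- That entrants from the other index studies are affected. Section 4.3.3.1 does not apply to them, so only the 6-week rule does.
- That the 6 weeks required before and after a live vaccine during the study (Sections 4.3.3 and 5.2.1) is a further contradiction. It governs interruption and restart, not the first dose. It is context only.
- That varicella has its own planned incidence rate. The SAP list names herpes zoster; varicella has no row of its own and would be counted under infections or serious infections.

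**What to change.** Reconcile Exclusion Criterion 16, Section 4.3.3 and Section 4.3.3.1 so that one interval applies to varicella vaccination before first dose. Alternatively, state in both Criterion 16 and Section 4.3.3 that 4.3.3.1 is a deliberate exception for A3921165 entrants, with the reason. Which interval applies is the sponsor's clinical decision.

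The cost is a sentence or two in the protocol, or a clarification letter to sites. No change to the SAP is needed.

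A separate listing in the study report of children dosed in the window is not needed. Protocol deviations are already to be listed there (SAP Appendix 1.13). Such a listing might not be feasible either: vaccination history is specified under medical history at the separate Screening visit (Section 6.1.1.1), and medical history is not among the procedures for those who roll over on the same day or within 14 days (Sections 6.1.2 and 6.1.3).

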4.3.3.2 Guidance regarding Household Contact Vaccine-Related Exposure

In accordance with the Infectious Disease Society of America's guidance for vaccination in immunocompromised individuals, the following is a guide for study subjects and their household contacts.

- i. Immunocompetent individuals who live in a household with the study subject can safely receive inactivated vaccines based on the standard of care vaccination schedules for children and adults or for travel (as defined by their country health ministry) or JIA guidelines.
- ii. Individuals who live in a household with a study subject should receive influenza vaccine annually. They can receive either: (a) inactivated influenza vaccine or (b) live attenuated influenza vaccine (LAIV) provided they are healthy and otherwise eligible.
- iii. Healthy immunocompetent individuals who live in a household with a study subject should receive the following live vaccines based on the CDC annual schedule: combined measles, mumps, and rubella (MMR) vaccines; rotavirus vaccine in infants aged 2–7 months; varicella vaccine; and zoster vaccine. Also, these individuals can safely receive the following vaccines for travel: yellow fever vaccine and oral typhoid vaccine.
- iv. Oral polio vaccine (OPV) **should not be administered** to individuals who live in a household with a study subject.
- v. Study subjects should avoid handling diapers of infants who have been vaccinated with rotavirus vaccine for 4 week after vaccination.
- vi. Immunocompromised patients should avoid contact with persons who develop skin lesions after receipt of varicella or zoster vaccination until the lesions clear

Subjects should avoid exposure to vaccinated or infected persons and contact the Investigator promptly should they develop signs and symptoms of infections.

4.3.4. Elective Surgery

During the course of this trial, no elective surgery should be scheduled without first consulting with the Pfizer Medical Monitor.

Subjects who do require surgery should temporarily discontinue study medication for at least one week prior to the surgical procedure and remain off study medication after the surgical

procedure until sutures/staples are removed, if the investigator determines this is clinically appropriate for the subject. If absorbing sutures or chemical closure methods are utilized, study medication can be resumed when the operative site is sufficiently healed and risk of infection is minimal.

4.3.5. Dietary Supplements

For the purposes of this protocol, dietary supplements are defined as vitamins, minerals, purified food substances, and herbals with pharmaceutical properties.

Vitamins, minerals and purified food substances are allowed in amounts not known to be associated with adverse effects (such as hypervitaminosis). Herbals must be discontinued for at least 4 weeks prior to first dose of study drug.

4.4. Sponsor Qualified Medical Personnel

The contact information for the sponsor's appropriately qualified medical personnel for the trial is documented in the study contact list located in the study manual.

To facilitate access to appropriately qualified medical personnel on study related medical questions or problems, subjects are provided with an emergency contact card. The card contains, at a minimum, protocol and investigational compound identifiers, subject study number, contact information for the investigational site and contact details for a help desk in the event that the investigational site staff cannot be reached to provide advice on a medical question or problem originating from another healthcare professional not involved in the subjects participation in the study. The help desk number can also be used by investigational staff if they are seeking advice on medical questions or problems, however it should only be used in the event that the established communication pathways between the investigational site and the study team are not available. It is therefore intended to augment, but not replace the established communication pathways between the investigational site and study team for advice on medical questions or problems that may arise during the study. The help desk number is not intended for use by the subject directly and if a subject calls that number they will be directed back to the investigational site.

